### **6.12.2. Extent of Exposure**

Exposure to therapy will be represented as either a complete or incomplete infusion, and will be summarized using descriptive statistics.

### **6.12.3. Adverse Events**

Summaries of AEs will include the number of patients with at least 1 AE for each treatment group. When reporting by System Organ Class (SOC) and PT, the reports will present the SOC in alphabetical order; while PTs within the SOC will be presented in order of overall decreasing frequency of occurrence overall. A patient with multiple AEs (different PTs) coded to the same SOC will be counted only once for that SOC, but will be counted each time for different PTs within that SOC. A patient with separate events of the same PT will be counted only once in the frequency tables for that PT.

Adverse events will be coded according to the Medical Dictionary for Regulatory Activities (MedDRA) and summarized by SOC, PT, severity, and relationship to IP as assessed by the investigator. For each event classification term, the number of subjects experiencing a treatment-emergent AE (TEAE) with that classification term will be tabulated.

In an overview table, the number and percentage of patients who experienced a TEAE, serious adverse event (SAE), AE related to study drug, died due to an AE, discontinued from the study treatment, or discontinued from the study due to an AE will be summarized by treatment.

Treatment-emergent AEs may be reported separately for the evaluation period and follow-up period.

#### **Treatment-Emergent Adverse Events**

A TEAE is defined as an event that first occurred or worsened in severity after baseline. The MedDRA Lowest Level Term (LLT) will be used in the treatment-emergent computation. The maximum severity for each LLT during the baseline period will be used as baseline. While unusual, it is possible to have a missing severity for events. For events with a missing severity during the baseline period, it will be treated as “mild” in severity for determining treatment emergence. Events with a missing severity during the postbaseline period will be treated as

“severe” and treatment emergence will be determined by comparing with baseline severity. Missing severity will be reported as missing, without imputation.

Additional types of AEs to be summarized are described in [Table PYAD 6.8](#).

**Table PYAD 6.8. Additional Types of Adverse Events to be Summarized**

Event Type	Summary Method
SAEs	SAEs will be summarized for each treatment arm by SOC and PT. These reports will also include the total number of SAE for each SOC and PT.
TEAEs Resulting in Death	If there are any TEAEs that result in death, a listing of all deaths will be provided. In addition, a summary table may also be created by PT in order of decreasing frequency of preferred term.
TEAEs Leading to Study Discontinuation	TEAEs for which the action taken is ‘Study Discontinuation’ will be identified as TEAEs that lead to study discontinuation. The TEAEs that lead to study discontinuation will be summarized for each treatment group by SOC and PT for the safety population. A by-patient listing of the TEAEs that lead to study discontinuation will also be provided.
Treatment-Related TEAEs	Every AE will be assessed by the investigator for its relationship to the randomly assigned study treatment.
TEAEs by Maximal Severity	Every AE will be graded by the investigator as mild, moderate, or severe, so for each patient the greatest severity observed can be obtained by comparing the severity of all a patient’s TEAEs that share the same SOC or PT. A table of TEAEs by maximal severity will be prepared for each treatment arm by SOC and PT.
TEAEs (Not Including Serious)	The most common nonserious TEAEs will be summarized. All PT that occur in at least 5% of the safety population patients in any treatment group, when not counting the serious TEAEs, will be tabulated by SOC and PT for each treatment group. These reports will also present the total number of TEAEs for each SOC and PT.

Abbreviations: AE = adverse event; PT = preferred term; SAE = serious adverse event; SOC = System Organ Class; TEAE = treatment-emergent adverse event.

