6.1.1.2. Management of Infusion Reactions

All participants should be monitored closely, as there is a risk of infusion reaction and hypersensitivity (including anaphylaxis) with any biological agent.

Symptoms and Signs

Symptoms and signs that may occur as part of an infusion reaction include, but are not limited to fever, chills, nausea, headache, bronchospasm, hypotension, angioedema, throat irritation, rash including urticaria, pruritus, myalgia, and dizziness.

Infusion-related reactions severity will be assessed and reported using the Division of AIDS (DAIDS) Table for Grading the Severity of Adult and Pediatric Adverse Events, Corrected Version 2.1 (July 2017).

This table describes the severity of reactions according to DAIDS.

Parameter	Mild	Moderate	Severe	Severe and Potentially Life-threatening
Acute Allergic Reaction	Localized urticaria (wheals) with no medical intervention indicated	Localized urticaria with intervention indicated OR Mild angioedema with no intervention indicated	Generalized Urticaria OR Angioedema with intervention indicated OR Symptoms of mild bronchospasm	Acute anaphylaxis OR Life-threatening bronchospasm OR Laryngeal edema
Cytokine Release Syndrome ^a	Mild signs and symptoms AND Therapy (that is, antibody infusion) interruption not indicated	Therapy (that is, antibody infusion) interruption indicated AND Responds promptly to symptomatic treatment OR	Prolonged severe signs and symptoms OR Recurrence of symptoms following initial improvement	Life-threatening consequences (for example, requiring pressor or ventilator support)

		Prophylactic medications indicated for ≤ 24 hours		
--	--	--	--	--

^a A disorder characterized by nausea, headache, tachycardia, hypotension, rash, and/or shortness of breath.

Source: DAIDS Table for Grading the Severity of Adult and Pediatric Adverse Events, Corrected Version 2.1 (July 2017).

Site Needs

The clinical site should have necessary equipment and medications for the management of any infusion reaction, which may include but is not limited to oxygen, IV fluids, epinephrine, acetaminophen and antihistamine.

Management of Infusion Reactions

Investigators should determine the severity of the infusion reaction and manage infusion reactions based on standard of care and their clinical judgment. If an infusion reaction occurs, then supportive care should be used in accordance with the signs and symptoms.

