10.3.3. Recording and Follow-Up of AE and/or SAE

AE and SAE Recording

- When an AE/SAE occurs, it is the responsibility of the investigator to review all documentation (e.g., hospital progress notes, laboratory reports, and diagnostics reports) related to the event.
- The investigator will then record all relevant AE/SAE information in the CRF.
- It is not acceptable for the investigator to send photocopies of the participant's medical records to Sponsor or designee in lieu of completion of the AE/SAE CRF page.
- There may be instances when copies of medical records for certain cases are requested by Sponsor or designee. In this case, all participant identifiers, with the exception of the participant number, will be redacted on the copies of the medical records before submission to Sponsor or designee.
- The investigator will attempt to establish a diagnosis of the event based on signs, symptoms, and/or other clinical information. Whenever possible, the diagnosis (not the individual signs/symptoms) will be documented as the AE/SAE.

Assessment of Intensity

The investigator will make an assessment of intensity for each non-infusion-related AE and SAE reported during the study and assign it to one of the following categories, which together with serious (i.e., SAE) criteria on the AE CRF ("results in death" and "life-threatening"), are aligned with the DAIDS *Table for Grading the Severity of Adult and Pediatric Adverse Events, Corrected Version 2.1 (July 2017)*.

Mild: Mild symptoms causing no or minimal interference with usual social and functional activities, with intervention not indicated.

Moderate: Moderate symptoms causing greater than minimal interference with usual social and functional activities, with intervention indicated.

Severe: Severe symptoms causing inability to perform usual social and functional activities, with intervention or hospitalization indicated.

Infusion-related AE/SAE intensity/severity should be assessed and graded according to protocol Section 6.1.1.2.

An event is defined as “serious” when it meets at least 1 of the predefined outcomes as described in the definition of an SAE, NOT when it is rated as severe.

Assessment of Causality

- The investigator is obligated to assess the relationship between study intervention and each AE/SAE.
- A “reasonable possibility” of a relationship conveys that there are facts, evidence, and/or arguments to suggest a causal relationship, rather than a relationship cannot be ruled out.

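### SAP Table PYAD 6.8 puts every adverse event on a three-level severity scale, but the protocol grades infusion-related events on four levels, and no specified by-arm output shows the fourth

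*SAP*

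**What the plan says.** **SAP, Section 6.12.3, Table PYAD 6.8.** The row on maximal severity states: "Every AE will be graded by the investigator as mild, moderate, or severe". It makes no exception for infusion-related events. The output follows from that premise: "A table of TEAEs by maximal severity will be prepared for each treatment arm by SOC and PT".

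**Protocol, Section 10.3.3.** The mild, moderate and severe categories have a stated scope: "The investigator will make an assessment of intensity for each non-infusion-related AE and SAE reported during the study". For the remaining events: "Infusion-related AE/SAE intensity/severity should be assessed and graded according to protocol Section 6.1.1.2".

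**Protocol, Section 6.1.1.2.** This section names the instrument: "Infusion-related reactions severity will be assessed and reported using the Division of AIDS (DAIDS) Table". The table printed there has four severity columns, the last being "Severe and Potentially Life-threatening". It has two rows, acute allergic reaction and cytokine release syndrome.

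**Other SAP outputs that bear on such events.** In Table PYAD 6.8, "SAEs will be summarized for each treatment arm by SOC and PT". Section 6.12.3 also plans an overview table that counts participants with SAEs by treatment. Section 6.12.4 plans a narrative for each participant with a death, an SAE or a treatment discontinuation due to an AE.

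**The concern.** Both documents describe how the same events are graded, and they disagree. The SAP's claim about every AE is wrong for infusion-related events, and it supplies no mapping from four grades to three.

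Each participant receives one infusion, so reactions to that infusion are the drug risk most directly tied to dosing. Protocol Section 2.3 reports that serious infusion-related reactions, some consistent with anaphylaxis, have been seen in ongoing LY3819253 studies. SAP Section 6.12 nevertheless specifies no separate summary of infusion-related or hypersensitivity reactions. The maximal-severity table is the only output whose severity levels the SAP defines, and those levels stop one grade short of the protocol's scale for these events.

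**Working it through.** The plan states no figure on this point, so the check compares the two scales and traces what a three-level table does with a fourth-grade event.

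1. **Levels and scope.** For non-infusion-related AEs, the protocol has 3 levels and the SAP has 3, so they agree. For infusion-related AEs, the protocol has 4 and the SAP has 3. The number of grades with no counterpart is 4 − 3 = 1, the top one.

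2. **Possible outcomes.** With no mapping rule, a fourth-grade event in a three-level table is either counted as severe or has no category. This is an inference, because the SAP does not say which, but a three-level table allows nothing else.

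3. **Where pooling hides something.** The table is arranged by system organ class and preferred term. Events with different terms sit on different rows, so pooling matters only when third- and fourth-grade events share a term. The Section 6.1.1.2 table shows how that can happen. Bronchospasm appears in both the third column (mild symptoms) and the fourth (life-threatening). Cytokine release syndrome also has an entry in both. In addition, protocol Section 8.3.6 encourages investigators to report qualifying events as an infusion-related immediate hypersensitivity reaction or a cytokine release-associated infusion reaction. Neither label carries a grade.

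4. **Hypothetical illustration.** Take cytokine release reactions reported under one term. Arm A has two that need pressor support (fourth grade). Arm B has two with prolonged severe symptoms (third grade).

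| Display | Arm A | Arm B | A − B at the highest level shown |
|---|---|---|---|
| Protocol, four grades | 0 severe, 2 fourth grade | 2 severe, 0 fourth grade | 2 − 0 = 2 |
| SAP, fourth grade pooled | 2 severe | 2 severe | 2 − 2 = 0 |
| SAP, fourth grade without a category | 0 severe | 2 severe | 0 − 2 = −2 |

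The counts are invented to show the mechanism and do not predict frequency. Pooling removes the contrast, and having no category reverses it.

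5. **Do other outputs recover the grade?** An immediately life-threatening AE is an SAE under protocol Section 10.3.2, so it should enter the SAE table. That table is not split by grade or by the reason for seriousness, and hospitalization alone can make an event serious. Narratives describe single cases and give no by-arm count. The event is therefore visible, but its grade is not tabulated.

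6. **A related sign.** For determining treatment emergence, SAP Section 6.12.3 treats a missing postbaseline severity as severe. That is the top of the SAP's scale but not of the protocol's infusion scale, which is consistent with the fourth grade not having been carried over.

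**The case against.** The strongest reply is that nothing important is lost. Life-threatening reactions are SAEs, tabulated by arm and by term, counted in the overview table and described in narratives. Under SAP Section 6.15.1 the DSMB sees unblinded AE and SAE summaries every month. Protocol Sections 8.3.6 and 8.3.7 also collect symptom detail for these reactions on the CRF. All of this stands, and it limits the point to one display.

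A reader might infer that anaphylaxis in one arm and generalized urticaria in the other would be indistinguishable. The documents do not support that: these are different event terms and would occupy separate preferred-term rows. A reader might also infer that the protocol mandates a study-report table by DAIDS grade. Section 6.1.1.2 concerns the management of infusion reactions and Section 10.3.3 concerns investigator recording. Both read most naturally as instructions on how sites grade and report events.

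Two further replies carry less weight. Section 10.3.3 says the three categories, "which together with serious (i.e., SAE) criteria on the AE CRF", align with DAIDS. This shows that the AE CRF holds a life-threatening criterion, but the sentence covers non-infusion-related events, and the SAP severity table does not use the criterion. SAP Section 6.12.3 also says in general terms that AEs are summarized by severity without naming levels. That does not rule out a four-level display, but it does not specify one; the levels are defined only in Table PYAD 6.8.

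Finally, adding a fourth row to the existing table would mix two scales wherever infusion-related and other events share a term. That objection is sound and shapes the fix.

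**Conclusion.** The SAP sentence is wrong as written for infusion-related events, and the two documents need to be reconciled. The gap is one grade out of four. It bites only where third- and fourth-grade events share a preferred term, and it affects the by-arm display of severity and nothing else. Efficacy results, alpha, power, data capture and safety oversight are unaffected. It would be too strong to conclude that life-threatening reactions would go unreported, given the SAE table, the narratives and the DSMB review.

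The conclusion assumes that sites grade infusion-related events as Section 10.3.3 directs, so that the fourth grade exists in the data, and that no mapping is set out in a document outside those provided. The number of events affected cannot be estimated from the documents and is probably small. The point is worth acting on because it concerns a named risk of the drug and the correction is cheap.

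**What to change.** In SAP Table PYAD 6.8, limit the three-level sentence to non-infusion-related AEs, matching protocol Section 10.3.3. Add a separate summary of infusion-related AEs by treatment arm within each part's Safety population, showing all four grades of protocol Section 6.1.1.2. Identify these events as those recorded on the infusion-related reaction/hypersensitivity CRF described in protocol Section 8.3.6, so that the flag is defined before the data are tabulated. Add a footnote to the maximal-severity table saying how infusion-related events are handled there. State how a missing grade is treated in the new summary.

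A separate summary is preferable to a fourth level in the existing table, because it keeps the two scales apart. The cost is a few lines of SAP text and one small extra safety table. No new data are needed, since the protocol already asks investigators for the grade.

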### SOC mapping

Medical Dictionary for Regulatory Activities PTs are assigned to a SOC through primary mappings (defined by MedDRA). Thus MedDRA PTs will appear in only 1 SOC.

### Events not summarized

Events considered related by the investigator will not be summarized. Medical representatives may use the relatedness assessment when reviewing individual cases.

#### **6.12.4. Deaths, Other Serious Adverse Events, and Other Notable Adverse Events**

The following are “notable” events, from start of study drug through end of study participation:

- Deaths
- SAEs, and
- Discontinuations of study treatment due to AEs.

Narratives (patient-level data and summary paragraph) will be provided for participants in the safety population with at least 1 notable event.

#### **6.12.5. Hospitalization, Clinical Events, and Clinical Status**

The following events (observed at any time point during the study evaluation period) will be summarized using descriptive statistics:

- Proportion of participants hospitalized
- Duration of hospitalization (DOH; in days),
- proportion (percentage) of participants admitted to Intensive Care Unit (ICU),
- proportion (percentage) of participants requiring mechanical ventilation (oxygen source = “Intubation/Mechanical Ventilation”)

All hospitalization events, and procedures of special interest will be listed.

In the event that a participant has an ongoing hospitalization event at the time of study disposition, the hospitalization end date will be imputed to the study disposition date.

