Additional manageable risks associated with most therapeutic monoclonal antibodies are the potential for infusion-related hypersensitivity and cytokine release reactions. The single infusion in this study will be administered at a controlled rate, the study participants will be monitored closely, and adjustments in the infusion rate will be made and/or the infusion stopped, if indicated. Additional information regarding infusion reaction management options is located in Section 6.1.1.2. As of 31 December 2020, approximately 4012 participants received blinded treatment of LY3819253 700 mg, 2800 mg, or 7000 mg, or placebo, of which approximately 3189 participants received LY3819253. Serious infusion-related reactions, including events consistent with anaphylaxis, were reported in these ongoing studies with LY3819253 (FDA EUA fact sheet 2020).

Clinical worsening of COVID-19 after administration of LY3819253 has been reported from post-authorization treatment within 24 hours of infusion. Signs and symptoms may include fever, hypoxia or increased respiratory difficulty, arrhythmia (e.g., atrial fibrillation, sinus tachycardia, and bradycardia), fatigue, and altered mental status. Some of these events required hospitalization. It is not known if these events were related to LY3819253 use or were due to progression of COVID-19.

Combination of LY3819253 and LY3832479

As of 04 November 2020, 542 participants in Study PYAB received blinded treatment of either placebo or the combination of 2800 mg LY3819253 and 2800 mg LY3832479. Three participants reported single immediate non-serious events of pruritis (2 events) and dyspnea (1 event).

Data from Study PYAB interim analysis indicate treatment with LY3819253 or the combination of LY3819253 and LY3832479 may decrease the risk of hospitalization in patients with mild to moderate COVID-19 (Chen et al. 2020; Gottlieb et al. 2020) thus providing benefit to patients with COVID-19.

Given the totality of data on LY3819253 and LY3832479, the well-established safety profile of other therapeutic mAbs, and the lack of disease directed therapeutic options for patients with COVID-19 illness or to prevent the SARS-CoV-2 infection, the overall benefit/risk assessment of this study is considered favorable.

More detailed information about the known and expected benefits and risks and reasonably expected adverse events of LY3819253 and LY3832479 may be found in each respective IB.

3. Objectives and Endpoints

Part 1

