10.3.1. Definition of AE

AE Definition

- An AE is any untoward medical occurrence in a patient or clinical study participant, temporally associated with the use of study intervention, whether or not considered related to the study intervention.
- NOTE: An AE can therefore be any unfavorable and unintended sign (including an abnormal laboratory finding), symptom, or disease (new or exacerbated) temporally associated with the use of study intervention.

Events Meeting the AE Definition

- Any abnormal laboratory test results (hematology, clinical chemistry, or urinalysis) or other safety assessments (e.g., electrocardiogram, radiological scans, vital signs measurements), including those that worsen from baseline, considered clinically significant in the medical and scientific judgment of the investigator (i.e., not related to progression of underlying disease).
- Exacerbation of a chronic or intermittent pre-existing condition including either an increase in frequency and/or intensity of the condition.
- New conditions detected or diagnosed after study intervention administration even though it may have been present before the start of the study.
- Signs, symptoms, or the clinical sequelae of a suspected drug-drug interaction.
- Signs, symptoms, or the clinical sequelae of a suspected overdose of either study intervention or a concomitant medication. Overdose per se will not be reported as an AE/SAE unless it is an intentional overdose taken with possible suicidal/self-harming intent. Such overdose should be reported regardless of sequelae.
- “Lack of efficacy” or “failure of expected pharmacological action” per se will not be reported as an AE or SAE. Such instances will be captured in the efficacy assessments. However, the signs, symptoms, and/or clinical sequelae resulting from lack of efficacy will be reported as AE or SAE if they fulfill the definition of an AE or SAE.

Events NOT Meeting the AE Definition

- The following study-specific clinical events related to COVID-19 are exempt from adverse event reporting unless the investigator deems the event to be related to the administration of study drug:
 - Hypoxemia due to COVID-19 requiring supplemental oxygen;
 - Hypoxemia due to COVID-19 requiring non-invasive ventilation or high flow oxygen devices;

- Respiratory failure due to COVID-19 requiring invasive mechanical ventilation or ECMO

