10.3.2. Definition of SAE

If an event is not an AE per definition above, then it cannot be an SAE even if serious conditions are met (e.g., hospitalization for signs/symptoms of the disease under study, death due to progression of disease).

An SAE is defined as any untoward medical occurrence that, at any dose:

a. Results in death

b. Is immediately life-threatening

The term “life-threatening” in the definition of “serious” refers to an event in which the participant was at risk of death at the time of the event. It does not refer to an event, which hypothetically might have caused death, if it were more severe.

c. Requires inpatient hospitalization or prolongation of existing hospitalization

- In general, hospitalization signifies that the participant has been admitted to hospital for observation and/or treatment that would not have been appropriate in the physician's office or outpatient setting. Complications that occur during hospitalization are AEs. If a complication prolongs hospitalization or fulfills any other serious criteria, the event is serious. When in doubt as to whether “hospitalization” occurred or was necessary, the AE should be considered serious.
- Hospitalization for elective treatment of a pre-existing condition that did not worsen from baseline is not considered an AE.

d. Results in persistent disability/incapacity

- The term disability means a substantial disruption of a person's ability to conduct normal life functions.

- This definition is not intended to include experiences of relatively minor medical significance such as uncomplicated headache, nausea, vomiting, diarrhea, influenza, and accidental trauma (e.g., sprained ankle) which may interfere with or prevent everyday life functions but do not constitute a substantial disruption.

e. Is a congenital anomaly/birth defect

f. Other situations:

- Medical or scientific judgment should be exercised in deciding whether SAE reporting is appropriate in other situations such as important medical events that may not be immediately life-threatening or result in death or hospitalization but may jeopardize the participant or may require medical or surgical intervention to prevent one of the other outcomes listed in the above definition. These events should usually be considered serious.

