- The investigator will use clinical judgment to determine the relationship.
- Alternative causes, such as underlying disease(s), concomitant therapy, and other risk factors, as well as the temporal relationship of the event to study intervention administration will be considered and investigated.
- The investigator will also consult the IB and/or Product Information, for marketed products, in his/her assessment.
- For each AE/SAE, the investigator **must** document in the medical notes that he/she has reviewed the AE/SAE and has provided an assessment of causality.
- There may be situations in which an SAE has occurred and the investigator has minimal information to include in the initial report to Sponsor or designee. However, it is very important that the investigator always make an assessment of causality for every event before the initial transmission of the SAE data to Sponsor or designee.
- The investigator may change his/her opinion of causality in light of follow-up information and send a SAE follow-up report with the updated causality assessment.
- The causality assessment is one of the criteria used when determining regulatory reporting requirements.

Follow-up of AEs and SAEs

- The investigator is obligated to perform or arrange for the conduct of supplemental measurements and/or evaluations as medically indicated or as requested by Sponsor or designee to elucidate the nature and/or causality of the AE or SAE as fully as possible.

This may include additional laboratory tests or investigations, histopathological examinations, or consultation with other health care professionals.

- If a participant dies during participation in the study or during a recognized follow-up period, the investigator will provide Sponsor or designee with a copy of any post-mortem findings including histopathology.
- New or updated information will be recorded in the originally completed CRF.
- The investigator will submit any updated SAE data to Sponsor or designee within 24 hours of receipt of the information.

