#### **6.12.7. Vital Signs and Other Physical Findings**

The planned summaries are provided in [Table PYAD.6.9](#). The measurements analyzed for vital signs and physical characteristics include systolic blood pressure (BP), diastolic BP, pulse, weight, and temperature.

The criteria for identifying subjects with treatment-emergent abnormalities are based on [Table PYAD.6.10](#).

Some of the analyses of vital signs may be incorporated into interactive display tools instead of or in addition to a static display. Any display described in [Table PYAD.6.9](#) and not provided would be available upon request. For example, box plots for observed values, scatter plots, and shift tables could be provided as interactive displays for medical review.

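### COVID-19 hypoxemia or respiratory failure starting within 24 hours of infusion, a named risk of unknown cause, escapes AE and SAE reporting unless the investigator attributes it to the drug

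*SAP*

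**What the plan says.** - **The risk.** Protocol 2.3: "Clinical worsening of COVID-19 after administration of LY3819253 has been reported from post-authorization treatment within 24 hours of infusion". Hypoxia is among the listed signs and some cases needed hospital care. On cause: "It is not known if these events were related to LY3819253 use or were due to progression of COVID-19".
- **The AE rule.** Protocol 10.3.1 names three COVID-19 events: hypoxemia needing supplemental oxygen, hypoxemia needing non-invasive ventilation or high-flow oxygen, and respiratory failure needing invasive ventilation or ECMO. These are "exempt from adverse event reporting unless the investigator deems the event to be related to the administration of study drug".
- **The SAE rule.** Protocol 10.3.2: "If an event is not an AE per definition above, then it cannot be an SAE even if serious conditions are met".
- **The attribution standard.** Under Protocol 10.3.3 the investigator needs facts, evidence or arguments "to suggest a causal relationship, rather than a relationship cannot be ruled out". Timing counts too: alternative causes "as well as the temporal relationship of the event to study intervention administration will be considered and investigated".
- **Event summary.** SAP 6.12.5: "The following events (observed at any time point during the study evaluation period) will be summarized using descriptive statistics". The items are hospitalization, its duration, ICU admission and mechanical ventilation.
- **Vital signs.** SAP 6.12.7: "The measurements analyzed for vital signs and physical characteristics include systolic blood pressure (BP), diastolic BP, pulse, weight, and temperature". Protocol 8.2.2 also counts respiration rate and SpO2 as vital signs, and Protocol 9.4.8 commits to analysing vital signs by visit.

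**The concern.** The protocol identifies a possible harm, gives its time window, and says nobody yet knows whether drug or disease is responsible. For the respiratory form of that harm, whether it enters the AE and SAE records depends on the investigator settling that same question case by case. An event left out because it looked like disease progression cannot later help to show whether the drug contributed.

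The stakes are highest in Part 3. Its participants enter with a positive test and all receive active drug. The current amendment opened it to recovered, vaccinated and antibody-treated people specifically to look at safety. Part 2 Treatment has the same visit schedule and also no placebo.

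**Working it through.** The plan states no figure on this point, so the check is mainly a comparison of sections.

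**1. Risk against reporting standard.** Protocol 2.3 leaves early worsening where a drug effect can be neither shown nor excluded. Protocol 10.3.3 says that inability to exclude a relationship is not enough. An investigator who applies both literally can leave the event unreported. The instruction to weigh timing will tip some cases into reporting, but not predictably.

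**2. How far the exemption reaches.** The attribution test covers only the three hypoxemia and respiratory-failure items. Fever, fatigue and other disease signs fall under a different rule (Protocol 8.1.2 and 10.3.1): they become AEs if worse than expected, with no drug-attribution test. Arrhythmia and altered mental status are not on the Protocol 8.1.2 symptom list and are not among the three items.

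**3. What else would show an early event** (Protocol 1.3 and 4.1.2).

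| Data source | Part 1 | Part 2 Treatment and Part 3 |
|---|---|---|
| Symptoms questionnaire | Daily | None |
| Scheduled vital signs after Day 1 | Daily to Day 57 | Day 8, Day 29, Day 85, unless hospitalized |
| ER visits and admissions, with dates | Yes | Yes |
| Placebo arm | Yes | No |

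In the right-hand column, hypoxemia treated with oxygen in the facility on Day 2, without an ER visit or admission and not judged drug-related, may appear only as an unscheduled vital-sign reading or a concomitant-therapy entry. The SAP 6.12.5 items would not count it.

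**4. What a clean Part 3 record could say.** Part 3 enrols 30 to about 500 at 1:1, so 30/2 = 15 to 500/2 = 250 per arm. With zero events the one-sided 95% upper bound is U = 1 − 0.05^(1/n).
- n = 15: U = 18.1%.
- n = 250: U = 1.2%.

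This presumes every event is recorded. If only a fraction c is recorded, the bound on the true rate is U/c. With c assumed at 50% it is 36.2% and 2.4%; at 25% it is 72.4% and 4.8%. The documents give no value for c.

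**5. What a Day 1–2 count could say in Part 1.** About 1700 randomized minus 1300 in the prevention population leaves at most 400, or 200 per arm. That remainder includes serology-positive, RT-PCR-negative people. If 25%, 50% or 100% of it is RT-PCR-positive (assumed), there are 50, 100 or 200 per arm.
- Zero-event bounds: 5.8%, 3.0%, 1.5%.
- Fisher's exact test, 5 versus 0 events: p = 0.056, 0.059, 0.061.
- Fisher's exact test, 6 versus 0 events: p = 0.027, 0.029, 0.030.

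Two-sided significance therefore needs 6 versus 0, that is 12%, 6% or 3% on drug. Such a count is descriptive.

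**6. Could the Part 1 21-day comparison hide early harm?** Let p be the placebo risk of moderate-or-worse disease, RR the drug's later risk ratio, and e an independent early excess on drug. The 21-day risks are equal when e = 1 − (1 − p)/(1 − RR·p). All inputs are assumed.
- p = 10%: e = 2.2% (RR 0.8) or 5.3% (RR 0.5).
- p = 20%: e = 4.8% (RR 0.8) or 11.1% (RR 0.5).

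This shows that masking is possible and nothing more.

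**The case against.** The other side has several good points.

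- **Early hospital events in Part 1 are largely visible already.** SAP 6.16.2.3 and 6.16.2.4 measure time to hospitalization and to ICU from the first positive test. In Part 1 Treatment that test is normally the Day 1 pre-dose swab, so the clock starts on infusion day. SAP 6.1.4 applies Kaplan-Meier to time-to-event analyses, so the curves at days 1 and 2 give those two events by arm against placebo. This stands. It leaves out ER visits and death. It does not carry over cleanly to Part 3, where the qualifying sample may be up to 10 days before infusion.
- **SpO2 and respiratory rate are already promised.** Protocol 8.2.2 with 9.4.8 covers them. The shorter SAP list is a misalignment between documents, not a decision to ignore oxygenation. This stands. The by-visit box plots in SAP Table PYAD.6.9 may also show Day 2 pulse and temperature in Part 1, if daily readings count as visits; the SAP does not say.
- **Other channels exist.** Participants are watched during infusion and for at least 1 hour after. Reactions within 6 hours believed to be hypersensitivity or cytokine release have their own CRF. The DSMB sees unblinded data monthly. These help in part. Worsening judged to be COVID-19 does not fit the reaction form, and the DSMB data list in SAP 6.15.1 does not name hospitalization events or clinical status.
- **Timing of the documents.** SAP Version 4 is dated 7-Dec-2020, while the risk section cites data to 31 December 2020. The SAP could not have reflected it, so this is an update still to be made. The DSMB charter and safety review plan are not available and may already hold a 24-hour summary.

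**Conclusion.** The concern holds in a narrow form. For three kinds of COVID-19 respiratory event, AE and SAE capture within 24 hours of infusion rests on a judgement that the protocol itself says cannot yet be made. The practical gap is new oxygen use inside the facility in Part 3 and Part 2 Treatment, without an ER visit or admission. Its size is unknown: the documents give neither a rate for early worsening nor a recording fraction, and the figures above only show what a record of given size and completeness could exclude.

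A reader might infer three stronger things. The documents support none of them.

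- **That all early worsening escapes safety reporting.** It does not: the attribution test covers three items, and other signs follow a different rule.
- **That the plan cannot see the first day or two at all.** Part 1 has daily vital signs and symptoms, and its hospitalization and ICU curves normally start on infusion day.
- **That Part 1's 21-day comparison conceals a harm.** The 2.2% to 11.1% range rests wholly on assumed risks and risk ratios.

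This is a cheap improvement in what is captured for a named risk, and it does not undermine the planned efficacy analyses.

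**What to change.** 1. **Protocol 10.3.1, prospectively.** State that the COVID-19 exemption does not apply to events starting within 24 hours of infusion, and that these are recorded whatever the attribution. Word it to override the expected-progression exclusion in the same section as well, or the same events could drop out by that route. It serves Part 3 and any further Part 2 enrolment; it cannot recover past Part 1 events. Cost: one sentence, then more AE records in infected participants. Some will be SAEs, with 24-hour reports (Protocol 8.3.1) and narratives (SAP 6.12.4). No new visits or samples.
2. **SAP 6.12.7.** Add SpO2 and respiratory rate, to match Protocol 8.2.2 and 9.4.8. For Part 1, show Day 2 change from pre-dose by arm, labelled post hoc if Part 1 is already unblinded. Cost: SAP wording and output from data already collected.
3. **SAP 6.12.5, optional.** Add a descriptive by-arm count of ER visit, hospitalization, ICU admission or death starting on Day 1 after dosing or on Day 2, in participants RT-PCR-positive at baseline. The Part 1 curves already give much of this, and the count would not pick up oxygen given in the facility, so it does not replace item 1.
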